6.3. Secondary Analysis Variables

6.3.1. Secondary Efficacy Variables

- Upper respiratory symptom score
- Lower respiratory symptom score
- ACQ-6 Score
- PEFR
- FEV₁

- FVC
- FeNO
- PC₂₀
- Virus load (via qPCR)

6.3.2. Secondary Mechanistic Variables

1. Blood & Sputum eosinophilia
2. Leukocyte numbers (e.g. ILC2, Th2) in BAL, blood and nasal scrapes measured by flow cytometry
3. Leukocyte numbers in immunohistochemistry-stained bronchial biopsies:
 - CRTH2+ cells (cells/mm² tissue)
 - In the submucosa
 - In the epithelium
 - EG2+ activated eosinophils (cells/mm² tissue)
 - In the submucosa
 - In the epithelium
4. Soluble Mediators (nasal and bronchial):
 - Prostaglandin D₂
 - Th2 cytokines (3): IL-4, IL-5, IL-13
 - Th1 cytokines (2): IFN- γ , IL-12p70
 - Th17 cytokines (4): IL-17A, IL-17F, GM-CSF, IL-22
 - Chemokines (7): Eotaxin, Eotaxin 3, IP-10, MDC, TARC, MIP-1 α , MIP-1 β
 - Pro-inflammatory markers (4): IL-6, IL-8, IL-1 β , TNF- α
 - Cytokines that can trigger type 2 inflammation (3): IL-25/-17E, IL-33, TSLP
 - Innate antiviral interferons (2): IFN- α , IL-29/IFN- λ 1
 - Additional (6): IL-9, IL-10, IL-15, IL-18, IL-23, MIP-3 α

6.3.3. Safety Analysis Variables

- Adverse events (recorded in free text; not coded)
- Serious adverse events
- Concomitant medications (recorded in free text, not coded)
- Vital signs (temperature, pulse, systolic/diastolic blood pressure, oxygen saturation levels, respiratory rate)
- Laboratory blood tests (full blood count, renal function, liver enzymes, clotting)

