1.2 RATIONALE FOR CURRENT STUDY

Hypothesis: This trial is designed to investigate the hypothesis that CRTH2 antagonism can prevent or attenuate the deterioration in symptoms in patients with asthma (i.e. asthma exacerbations) following rhinovirus infection.

Rationale for using the RV-induced asthma exacerbation model

The RV-induced asthma exacerbation model offers the ability to investigate treatment effects on exacerbations with a small number of volunteers, minimising the numbers exposed to a novel agent with limited safety data. In contrast, trials of therapies powered to evaluate an effect on naturally occurring exacerbations require several hundred volunteers, a long study period to capture enough events and are significantly more expensive to carry out.

The RV-induced exacerbation model has been used extensively around the world over >15 years, including four studies by [name] group [9, 10, 14, 15], and is well-established with an excellent safety profile (reviewed in [16]); across the studies at Imperial there have been no adverse events, and no need for hospitalisation or systemic corticosteroids during the infection. Moreover, the RV-induced exacerbation model uniquely provides the opportunity to select a well-defined sample population, use a uniform viral challenge, and sample repeatedly as the exacerbation evolves, allowing accurate dissection of the timings of responses and their relationship to viral load.

Rationale for using the CRTH2 antagonist OC459

As of August 2013, at least 12 CRTH2 antagonists were in active clinical development [17]. Of these, OC459 (Atopix Therapeutics Ltd) had been trialled for the longest duration in a phase 2 study (17 weeks). In total, 637 patients across five published studies have been exposed to OC459 [18-22], including 482 patients with asthma, with an excellent safety record. OC459 has therefore been chosen for further study from the available CRTH2 antagonists due to its safety profile; there is no reason to think that is more or less effective than any other CRTH2 antagonist.

In addition, the largest study of OC459 to date suggested that it may be effective in reducing exacerbations: a trend towards reduction in asthma exacerbations was noted, with a 3.8% incidence in the pooled dose groups compared to 7.7% on placebo ($p=0.107$) [22]. A dose of 25 mg once daily was as effective as the other doses (100mg twice daily and 200mg once daily) in this study.

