7 INVESTIGATIONAL MEDICINAL PRODUCT (IMP)

7.1 IMP DESCRIPTION

OC459 is a once-daily oral, highly potent and selective CRTH2 antagonist which is active on both the recombinant and native human receptor.

The integrated safety database for OC459 includes data for a total of 754 subjects who received OC459 for up to 3 months with more than 500 subjects receiving doses ≥ 100 mg daily. The overall incidence of adverse events was similar for those treated with OC459 (28.2%) compared to placebo (26.7%) and few subjects in either group had serious adverse events (0.1% and 0.5% for OC459 and placebo respectively). The adverse event profile after OC459 administration was generally comparable to that after placebo; the most common adverse event reported was headache (6.6% vs 5.1% for OC459 and placebo, respectively).

OC459 repeat doses of up to 400mg have been studied in patients and no clear dose ordered effects on safety have been observed. Furthermore, no end organ toxicology or significant changes in clinical chemistry (including liver enzymes) have been observed in non-clinical toxicology studies including long term studies conducted at very high doses in the mouse (3 month dosing), rat (six months dosing) and the dog (12 month dosing). The known metabolites of OC459 have been detected in at least one species including the acylglucuronide of OC459 which is the major metabolite in humans.

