9.4 CLINICAL SYMPTOM SCORES (INCLUDING ACQ)

Patients will be required to keep a diary card of both upper and lower respiratory tract symptoms during the study period (see Appendices). The diary cards will be commenced 21 days prior to inoculation (on day -21) to derive a baseline symptom score. Symptom scores will be kept daily for 6 weeks post-inoculation until the convalescent visit. Spirometry measurements and drug compliance will be recorded on the same diary cards.

Upper Respiratory Tract Symptoms

The diary card of upper respiratory tract symptoms will be started 21 days prior to inoculation. A total upper respiratory clinical symptom score will be derived using a scale of 0 to 3 (absent, mild, moderate and severe) for each of the following eight respiratory symptoms: sneezing, headache, malaise, fever/chills, nasal discharge, nasal obstruction, sore throat and cough, according to previously established criteria [23]. Symptoms will be recorded at the same time of day and before any procedures such as bronchoscopy are performed. An example is shown below:

Symptom	Day 1	Day 2	Day 3	Day 4	Day 5	Day 6	Day 7
Sneezing							
Headache							
Malaise							

Fever/chills							
Nasal discharge							
Nasal obstruction							
Sore throat							
Cough							
Total score							

0 = absent, 1 = mild, 2 = moderate, 3 = severe

The maximum clinical severity score on any one day would be 24. Individual symptom scores will be accumulated over the six-day period from the onset of the cold and the recording on the day prior to inoculation subtracted. Thus, for a patient who has a score of zero on day -1 prior to inoculation, the maximum cumulative score for the six days is 144.

Lower Respiratory Tract Symptoms

A diary card of lower respiratory tract symptoms will be completed with a scoring system as outlined below:

Symptom	Day 1	Day 2	Day 3	Day 4	Day 5	Day 6	Day 7
Cough on waking							
Wheeze on waking							
Daytime cough							
Daytime wheeze							
Daytime breathlessness							
Nocturnal cough, wheeze, breathlessness							
Total score							

0 = absent, 1 = mild, 2 = moderate, 3 = severe

An exacerbation of asthma is defined as an increase in the total respiratory score of at least 2 points over baseline on 2 consecutive days.

Asthma Control Questionnaire (ACQ)

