9.14 BRONCHOSCOPY

Bronchoscopies will be performed on study visits as per Table 1 in the endoscopy suite at St Mary's Hospital, in accordance with British Thoracic Society (BTS) guidelines [26]:

- Subjects will sign a consent form on entering the study and will sign a separate consent form for each bronchoscopy. The procedure will be explained during the assessment stage and subjects will be given written information specifically regarding bronchoscopies in addition to the Participant Information Sheet.
- Subjects will fast for six hours prior to the procedure.
- Resuscitation equipment (for intubation, ECG monitoring and defibrillation) and necessary drugs (salbutamol, theophylline, adrenaline, hydrocortisone) will be available in the bronchoscopy room.
- Premedication will be given including:
 - Nebulised salbutamol 2.5mg prior to bronchoscopy
 - Sedation with midazolam (2-10mg) and/or fentanyl (25-200mcg) as necessary
 - Lignocaine spray (10%) and solutions (1%) for topical anaesthesia. The total dose will not exceed 7mg/kg or 400mg in total.
- Supplemental oxygen at a rate of 2Lmin⁻¹ is given via a nasal cannula and oxygen saturations and heart rate are monitored with a pulse oximeter continuously. Intravenous access will be mandatory in all cases.
- The subject will be monitored during the bronchoscopy by a separate nurse and a second suitably qualified physician will be present to act as an advocate.
- The following samples will be collected in this order:
 1. Bronchosorption using Synthetic Absorptive Matrix (SAM)
 2. Bronchial brushings
 3. Bronchoalveolar lavage (BAL)
 4. Bronchial biopsy

At the second bronchoscopy, sampling should be performed on the contralateral side to the analogous procedures done at the first bronchoscopy.

- All adverse events (pain, bleeding, hypoxia etc) will be recorded.
- Subjects will be observed for 1-2 hours, nil by mouth, after the procedure.
- Transportation will be arranged as subjects should not drive on the day of the procedure.
- All subjects will have a contact telephone number on discharge.

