7.3.4. Safety Analysis

Adverse events will be summarised by treatment and severity. Separate tables summarising adverse events and their relationship to study treatment as well as summarising adverse events by treatment and timepoint will also be produced.

Serious adverse events will be listed and summarised by site, category and treatment. Separate tables will also be produced summarising serious adverse events and their relationship to study treatment as well as summarising serious adverse events by treatment and timepoint.

Vital Signs and Laboratory blood tests will be summarized by treatment per visit and will be presented as means and standard deviations if data is consistent with that from a normal population distribution, and as medians and inter-quartile ranges for data that is inconsistent. Categorical variables will be presented as frequencies and percentages.

If it is deemed appropriate, treatment effect will be assessed via t-test for continuous variables and Chi-square test or Fisher exact test for categorical variables (with the appropriate generalized linear model being used).

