***Table Note: Where subjects have more than one SAE the highest relationship has been used.**

Table 3.30 - Summary of Vital Signs Results

Laboratory Test (units)*	Treatment	Visit	n	Mean	SD	Median	Min.	Max.
xxxxx (xxxx)	Control							
	Treatment							

*Variables for inclusion as per section 6.3.4

Table 3.31 - Summary of Clinical Chemistry & Haematology Results

Laboratory Test (units)*	Treatment	Visit	n	Mean	SD	Median	Min.	Max.
xxxxx (xxxx)	Control							
	Treatment							

*Variables for inclusion as per section 6.3.4

Exploratory Analysis

Table 4.xx - Exploratory Analyses as required

Extent of output determined by Section 7.4

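### No planned output shows which non-serious adverse events occurred in each arm, and the period rows of Tables 3.23 and 3.27 do not fit the dosing schedule

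*SAP*

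**What the plan says.** Safety of OC459 is a secondary objective (Protocol 2; SAP 2.2), and AE reporting is the first safety item in SAP 3.2. SAP 6.3.3 gives the variable as "Adverse events (recorded in free text; not coded". For analysis, SAP 7.3.4 states that "Adverse events will be summarised by treatment and severity", and adds tables by relationship to treatment and by timepoint. Serious events get more: "Serious adverse events will be listed and summarised by site, category and treatment".

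The shells for Tables 3.23 and 3.27 use four period rows: Pre-Treatment (Wk1), Pre-Inoculation (Wk2), Assessment Phase (Wk3-4) and Follow-Up (Wk5-9). Under Protocol 9.1, study drug starts at randomisation on Day -21 and continues through inoculation on Day 0. It stops on Day 14, and the last visit is on Day 42.

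**The concern.** Two arms with the same number of mild or moderate events could have had quite different events, and a reader of the planned tables could not tell. The totals also combine sources. Protocol 9.14 says of bronchoscopy that "All adverse events (pain, bleeding, hypoxia etc) will be recorded", and each subject has two bronchoscopies. Whether cold symptoms from the challenge also enter the AE record is unclear, because the diary already collects them (Protocol 9.4). Relationship grading separates these sources only in part and names no event.

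The period rows add a second problem. A timepoint table should separate drug alone, drug plus virus, and the off-drug period. Read literally, these rows label on-drug events as pre-treatment and some on-drug, post-virus events as follow-up.

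**Working it through.** The plan states no figure to reproduce. The check has two parts.

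**1. Inventory of safety outputs (SAP Appendices A and B)**

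| Output | Covers | Names a non-serious event by arm? |
|---|---|---|
| 3.23 | All AEs by timepoint | No |
| 3.24 | All AEs by severity; also the seriousness criterion for SAEs | No |
| 3.25 | All AEs by relationship | No |
| 3.26 | SAE listing with a diagnosis column | No, SAEs only |
| 3.27 to 3.29 | SAEs by timepoint, severity and relationship | No, SAEs only |
| 3.30 | Vital signs | No |
| 3.31 | Laboratory results | No |

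Count: 3 + 1 + 3 + 1 + 1 = 9 outputs, of which 0 name a non-serious event.

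Three other places could have filled the gap, and none does:
- The summary by category in 7.3.4 applies to SAEs only.
- The open-ended exploratory Table 4.xx carries the note "Extent of output determined by Section 7.4", and Section 7.4 contains no AE analysis.
- The optional tests at the end of 7.3.4 name no AE type as a variable.

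The terms themselves will exist: Protocol 8.3.1 has all non-serious events recorded on the case report form.

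**2. Period rows against the schedule (Protocol 9.1 and Table 1; SAP 4.2)**

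Actual periods, counting Day 0 as post-virus:
- On drug, before virus: Day -21 to -1 = 21 days, which is 21/7 = 3 weeks.
- On drug, after virus: Day 0 to 14 = 15 days.
- Off drug: Day 15 to 42 = 28 days.

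Week labels under three possible numberings:

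| Week 1 begins | Pre-Treatment (Wk1) | Pre-Inoculation (Wk2) | Assessment (Wk3-4) | Follow-Up (Wk5-9) |
|---|---|---|---|---|
| At randomisation | Day -21 to -15, all on drug | Day -14 to -8 | Day -7 to 6 | From Day 7 |
| So that Wk3 starts at inoculation | Day -14 to -8, all on drug | Day -7 to -1 | Day 0 to 13 | From Day 14 |
| One week before randomisation | Day -28 to -22 | Day -21 to -15 | Day -14 to -1, no post-virus day | From Day 0 |

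The first numbering is the natural one, since SAP 4.2 gives nine weeks from randomisation and the rows end at week 9. It puts on-drug Days 7 to 14 (14 - 7 + 1 = 8 days) in Follow-Up. The second leaves Day -21 to -15 without a row. The third puts the whole post-virus dosing period in Follow-Up. No other shift can work: the labels leave one week between Pre-Treatment and Assessment Phase, but three weeks of dosing precede inoculation.

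**The case against.** The strongest reply is that the promised outcome is delivered. Protocol 3.1 sets the safety outcome as the difference in the number of AEs, and Tables 3.23 to 3.25 count events and patients by arm. SAEs are listed by arm with a diagnosis, and vital signs and laboratory results are summarised by arm. Both arms follow the same schedule under double-blind 1:1 allocation, so mixing procedure and drug events in the totals does not by itself bias the comparison. All of this stands, and it limits the point to description.

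A second reply is that a by-term display tells little at this size. That is true for inference. If 0 of 22 subjects report a term, the one-sided 95% upper bound is 1 - 0.05^(1/22) = 12.7%. This argues against testing terms, not against showing them.

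A third reply is that an analyst may follow the phase names and ignore the week numbers. The split would then be right and only the labels wrong. The shells need correcting either way.

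A reader might also infer that a by-term table would let this trial be compared with the OC459 safety database, in which "the most common adverse event reported was headache (6.6% vs 5.1% for OC459 and placebo, respectively" (Protocol 7.1). The documents do not support that. The diary symptoms scored for colds are "sneezing, headache, malaise, fever/chills, nasal discharge, nasal obstruction, sore throat and cough" (Protocol 9.4), so headache here could be raised by the induced cold, or reduced in the AE record if it stays in the diary. The trial also adds two bronchoscopies. The remark in Protocol 1.2 that "across the studies at Imperial there have been no adverse events" concerns past studies and does not settle what will be recorded in this one.

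**Conclusion.** The point holds as a reporting gap with a shell error. None of the nine planned safety outputs shows which non-serious events occurred in each arm. The period rows of Tables 3.23 and 3.27 fit the schedule under no week numbering.

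It would go too far to say that the safety objective fails, or that a fixed share of events will be misclassified. Under the numbering from randomisation, the Pre-Inoculation row holds 7 of 21 pre-virus days (33%) and 8 on-drug days fall in Follow-Up. Those figures apply only if the labels are read literally from randomisation. The number-of-AEs outcome, SAE reporting, the primary endpoint and the sample size are unaffected.

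The conclusion assumes that the appendices list all planned safety outputs and that 22 subjects per arm are enrolled.

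**What to change.** 1. Replace the rows of Tables 3.23 and 3.27 with periods defined by study day of onset:
   - before first dose, if any such events exist;
   - Day -21 to inoculation (on drug, before virus);
   - inoculation to Day 14 (on drug, after virus);
   - Day 15 to Day 42 (off drug).
2. Add to SAP 7.3.4 and Appendix A one descriptive by-arm output of AE terms in the safety analysis set, with no hypothesis test. Either form would do: a listing of all AEs on the pattern of Table 3.26, or a simple table of subjects and events by verbatim term, grouped by the clinical team before unblinding. If the table is chosen, amend the wording in 6.3.3 to describe the grouping. Dictionary coding is not needed.

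Cost: SAP wording, new row labels in two shells, one extra output, and an estimated few hours of work for 44 subjects. No new data are required. Two limits remain. There is almost no power for any single term at 22 per arm. The pre-virus period still contains the Day -8 bronchoscopy, although its events would appear under their own terms.

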6.4. Exploratory Analysis Variables

Exploratory analysis will take place across all cell counts obtained above using flow cytometry and bronchial biopsy from blood, nasal and bronchoscopic samples: A comprehensive list of which can be found below:

- Total viable cells
- Total CRTH2+ cells

- Th2 cells (defined as CD3+CD4+CRTH2+)
 - Of which are also GATA3+
- Eosinophils (defined as CD66b+CD16-)
- Neutrophils (defined as CD66b+CD16+)
- Mast cells (defined as FcERI+Lin-CRTH2-CD117+)
- Basophils (defined as FcERI+Lin-CRTH2+CD117-)
- ILC2 cells (defined as Lin-CD127+FcERI-CRTH2+)
- ILC1 cells (defined as Lin-CD127+FcERI-CRTH2-CD117-)
- ILC3 cells (defined as Lin-CD127+FcERI-CRTH2-CD117+)

Blood samples will be assessed at day -21, day -8, day 5, day 42; nasal samples at day -21, day -8, day 5 and bronchoscopic samples at day -8, day 5 (counted by flow cytometry)

Further exploratory analysis will take place on cells obtained from bronchial biopsies from day -8 and day 5 by immunohistochemistry:

- CRTH2+ cells (cells/mm² tissue)
 - In the submucosa
 - In the epithelium
- EG2+ activated eosinophils (cells/mm² tissue)
 - In the submucosa
 - In the epithelium

Values for ACQ-6 (D-9, D10) will also be analysed.

In addition, exploratory analysis will take place to investigate antiviral response. This will consist of the following variables:

- Protein levels of IFN- β , - λ 1 and - λ 2/3 in supernatants of cells taken from subjects and infected with virus *ex vivo*.
- mRNA levels of IFN- β , - λ 1 and - λ 2/3 a panel of interferon stimulated genes (Mx1, RIG-I, OAS, viperin, IP-10, PKC) in cell lysates from the same *ex vivo* experiments.

7. Statistical Methodology

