7.4. Exploratory Analysis

7.4.1. Exploratory Mechanistic Testing

Analysis to investigate any difference in effect of OC459 and placebo for the exploratory analyses below will be performed using the difference in values via unpaired (two-sample) t-test or Mann-Whitney U tests for non-parametric data.

- Changes in inflammatory cell counts by flow cytometry after drug treatment but before virus inoculation (for blood and nasal samples, not bronchial): Day -21 to Day -8.
- Changes in soluble mediators after drug treatment but before virus inoculation (nasal samples): Day -21 to Day 0.
- Changes in cell counts from bronchial biopsies taken at Day -8 and Day 5 will also be assessed CRTH2+ cells (cells/mm² tissue) & EG2+ activated eosinophils (cells/mm² tissue).

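### SAP 6.4 defines six of eight marker-defined cell types by CRTH2, the receptor OC459 acts on, so the planned counts could not separate altered CRTH2 staining from altered recruitment

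*SAP*

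**What the plan says.** Protocol 7.1 describes OC459 as a "highly potent and selective CRTH2 antagonist which is active on both the recombinant and native human receptor".

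SAP 6.4 gives marker definitions for eight cell types. Three require CRTH2 to be present: "Th2 cells (defined as CD3+CD4+CRTH2" positive, "ILC2 cells (defined as Lin-CD127+FcERI-CRTH2" positive, and "Basophils (defined as FcERI+Lin-CRTH2+CD117" negative. Three require it to be absent: "Mast cells (defined as FcERI+Lin-CRTH2-CD117" positive, "ILC1 cells (defined as Lin-CD127+FcERI-CRTH2-CD117" negative, and ILC3, which has the ILC1 definition but is CD117-positive. Only eosinophils (CD66b+CD16-) and neutrophils (CD66b+CD16+) are defined without CRTH2. The GATA3 count is a sub-item of the Th2 line ("Of which are also GATA3" positive), so it covers only cells already called CRTH2-positive. The same section also lists total CRTH2+ cells and biopsy CRTH2+ cells.

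These counts serve the secondary objective on immune-cell recruitment (SAP 2.2) and are reported as leukocyte numbers (SAP 6.3.2). SAP 7.3.2 compares the arms on the Day -8 to Day 5 difference. SAP 7.4.1 tests "Changes in inflammatory cell counts by flow cytometry after drug treatment but before virus inoculation", from Day -21 to Day -8, in blood and nasal samples only. Dosing runs from Day -21 to Day 14 (SAP 4.9).

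Neither document describes a staining-interference check, a count of the six types that does not use CRTH2, or a sensitivity analysis on these definitions.

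**The concern.** The mechanistic question is whether OC459 changes how many ILC2, Th2 and related cells reach the airway. The marker used to recognise those cells is the drug's own target. If the drug altered the amount of CRTH2 detectable on a cell, that cell would be reclassified without having moved: an ILC2 would be counted as an ILC1 or ILC3 according to CD117, and a Th2 cell or basophil would leave its count. GATA3 could not reveal this, because a Th2 cell that loses CRTH2 staining is lost from the GATA3 sub-count as well.

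A staining change could then be reported as part of the mechanism of action, or could mask a true effect on recruitment.

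**Working it through.** The documents give no figure for this point, so there is none to reproduce. The check has four steps.

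**1. Dependence on CRTH2.** Of the eight types in SAP 6.4, 3 are CRTH2-positive, 3 are CRTH2-negative and 2 do not use it: 3 + 3 = 6 of 8.

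**2. Where a reclassified cell goes.** The ILC definitions divide Lin-CD127+FcERI- cells into CRTH2+ (ILC2), CRTH2-CD117- (ILC1) and CRTH2-CD117+ (ILC3). Their sum is therefore all Lin-CD127+FcERI- cells, whatever happens to CRTH2. As an example, assume 100 cells of each type and lost ILC2 split equally by CD117. With 25% loss, ILC2 = 100 × 0.75 = 75, and ILC1 and ILC3 are each 100 + 12.5 = 112.5; the total stays at 300. Basophils differ: they are CD117-negative, so one that loses CRTH2 does not meet the mast-cell definition and simply drops out. Mast-cell counts could change only through CRTH2+CD117+ cells.

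**3. Day -21 to Day -8 (SAP 7.4.1).** Day -21 is the first dosing day (I assume sampling precedes the first dose) and Day -8 is on drug, so the full staining loss enters the change. Illustration: 15 per arm (the evaluable number in SAP 4.4), no true effect, log change distributed N(0, SD) on placebo and N(log(1 − r), SD) on OC459, two-sided Mann-Whitney at 5%. The loss r and the SDs are assumptions. Chance of P < 0.05:

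| SD of log change | r = 10% | 20% | 30% | 40% |
|---|---|---|---|---|
| 0.3 | 14% | 47% | 86% | 99% |
| 0.5 | 8% | 20% | 43% | 73% |
| 0.7 | 6% | 12% | 25% | 46% |

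At r = 0 the rate is nominal. The SAP tests the raw difference, not the log change. On raw differences (between-subject log SD 0.5; within-subject log SD 0.2 or 0.4) the rates are 14% or 7% at 10% loss, 64% or 20% at 25%, and 99% or 68% at 50%.

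**4. Day -8 to Day 5 (SAP 7.3.2).** Both days are on drug. With true counts A and B and a constant loss L, the observed difference is (1 − L)B − (1 − L)A = (1 − L)(B − A). The loss rescales the change and does not create one: at L = 25%, a rise of 100 reads as 75. Under the raw-difference assumptions of step 3, rates stay at about 4–5% for L up to 50% if infection does not change the counts. If counts truly double in both arms, they are about 16% or 9% at 25% loss and 68% or 30% at 50% loss.

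**The case against.** The strongest objection is that the causal premise is absent. Protocol 7.1 says OC459 acts on the native receptor. It does not say that the drug blocks the detecting antibody or alters surface CRTH2, and zero loss is as compatible with the documents as 40%. Antibody choice and interference checks may also sit in a laboratory manual that is not part of these documents. This stands, and it is why the point is conditional.

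Existing outputs give some protection. ILC1, ILC2 and ILC3 are all reported, so a reciprocal shift could be noticed. Blood is also assessed at Day 42, four weeks after dosing stops. Eosinophils, neutrophils, EG2+ cells and the type 2 cytokines do not depend on CRTH2. This stands in part: SAP 7.3.2 and 7.4.1 name no comparison using Day 42 cell counts, nothing tells the analyst to sum the ILC types, and no output covers a Th2 cell that has lost CRTH2 staining.

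The illustration does not match the planned analysis exactly. Pre-infection mechanistic effects use the extended set (SAP 5.4), which includes uninfected completers, so 15 per arm is not the planned number; a larger number would raise the rates.

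A reader might infer that the high rates in the first table apply to the secondary mechanistic analysis. They do not, because both of its time points are on drug. A reader might also infer that an ILC2 finding should be accepted only if total ILCs move the same way. That rule would hide true effects. Suppose ILC2 truly fall by 40% (log SD 0.5, 15 per arm). If ILC2 are 10%, 20% or 33% of ILCs, the total falls by only 4%, 8% or 13% (0.40 × share). The median total then points the right way in about 57% to 73% of trials, with power of 5% to 11%.

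**Conclusion.** The point holds in conditional form. As defined, the planned flow-cytometry counts for six cell types could not distinguish a change in recruitment from a change in CRTH2 staining, and the plan has no readout that would separate them for ILC2 or Th2 cells. Whether OC459 alters staining is unknown from the documents, so this is a possible bias of unknown size. A reading that the counts are biased is not supported.

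If staining does change, the exploratory Day -21 to Day -8 comparison is the most exposed, with false-positive rates from near nominal to almost certain depending on the assumed loss and SD. The secondary Day -8 to Day 5 comparison is affected by a constant loss only to the extent that infection changes the counts. Total CRTH2+ cells and biopsy CRTH2+ counts share the dependence; the route for mast cells is narrow. The primary symptom score is not touched, and the SAP already asks for more cautious interpretation beyond the primary outcome. This is a worthwhile, inexpensive improvement to the mechanistic analysis.

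**What to change.** In SAP 6.4, 7.3.2 and 7.4.1, add two supportive sensitivity readouts from the flow data already collected, beside the existing counts:

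- total ILCs, Lin-CD127+FcERI-, which is the sum of the three ILC counts as defined;
- CD3+CD4+GATA3+ cells regardless of CRTH2.

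State in advance that a fall in ILC2 with a matching rise in ILC1 or ILC3 and an unchanged total will be described as possibly a CRTH2 staining change. Put the same caveat on basophils, total CRTH2+ cells and biopsy CRTH2+ counts, for which these additions give no separate readout. Do not make any recruitment conclusion conditional on total ILCs moving the same way.

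The cost is SAP wording and a little re-analysis of existing flow files, with no new samples or visits. The limitation is that total ILCs are insensitive when ILC2 are a small share of them, so an unchanged total does not by itself rule out a true ILC2 effect.
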